7.1 Subject Inclusion Criteria

To qualify for inclusion in this study, subjects must:

1. Be healthy, immunocompetent males or females ≥ 18 years of age
2. Present with ≥ 2 and ≤ 30 external genital and/or perianal warts in ≥ 1 of the following anatomic areas:
 - a. In both sexes: medial thigh (except inguinal fold); supra-pubic, perineal, and perianal areas
 - b. In men: over the glans penis (excluding urethral meatus), penis shaft, scrotum, and foreskin
 - c. In women: vulva (excluding labia minora and mucosal surfaces)
3. Have warts present for ≥ 4 weeks at the baseline visit
4. Have warts that are ≤ 8 mm in diameter each with a total wart area (i.e., all warts combined) ≥ 10 mm²
5. Be free of any systemic or dermatologic disorder, that, in the opinion of the Investigator, will interfere with the study conduct, efficacy assessments, or increase the subject's risk of AEs
6. Refrain from swimming, bathing, or prolonged immersion in water or any other liquids until the study drug is removed
7. Have the ability to follow study instructions and be likely to complete all study requirements

8. Agree to use no wart-removing product (prescription or over-the-counter, including any HPV immunization) other than the study drug during the course of the study
9. Provide written informed consent in a manner approved by the IRB and evidenced by the signature on an IRB approved consent form
10. Provide written authorization for use and disclosure of protected health information
11. If participating in the optional photographic portion of the study, agree to allow photographs of warts to be taken at each treatment and all follow-up visit by the research team

7.2 Subject Exclusion Criteria

Candidates will be excluded from the study if they:

1. Are unable to cooperate with the requirements or visits of the study, as determined by the Investigator
2. Have a wart within the allowed treatment area > 8 mm in diameter or with an eroded or ulcerated surface, in the Investigator's opinion
3. Have an unclear diagnosis of condyloma
4. Have warts outside of the allowed treatment area (e.g., cervical, vaginal, clitoral, rectal, within 2 mm of anus) that require treatment during the planned study period or are undergoing treatment in the last 4 weeks
5. Have any wart types other than genital warts (e.g., common or plantar warts) that require treatment during the study period
6. Have a history of genital infections or diseases within 4 weeks before enrollment
7. Have active genital herpes eruption, or had active genital herpes lesions within 4 weeks before enrollment
8. Have a history of HPV-associated malignancies within the last 5 years

-
9. Have a dermatologic disease (e.g., psoriasis) or skin condition in the wart areas that may cause difficulty with examination
 10. Are systemically immunosuppressed or have required, or will require, systemic immunosuppressive or immunomodulatory medication (including oral or parenteral corticosteroids) within 30 days before enrollment or during the course of the study (routine use of local [e.g., topical, inhaled, or intranasal] corticosteroids during the study is allowed)
 11. Have any chronic or acute medical condition that, in the opinion of the Investigator, may interfere with the study results or place the subject at undue risk (e.g., human immunodeficiency virus, systemic lupus erythematosus, viral hepatitis, diabetes, clinically significant medical, psychiatric, or emotional condition or abnormality).
 12. Have had HPV immunization within the last 3 months prior to enrollment. (NOTE: HPV may NOT be administered during the course of the trial. Other immunizations (e.g., flu shots) may be administered throughout the study, but not within 5 days before or after treatment.
 13. Have had any previous treatment (including an investigational agent in a clinical trial) of genital warts, including but not limited to the use of imiquimod, antivirals, retinoids, salicylic acid, lactic acid, hydrogen peroxide, iodine-based or nitric oxide-based therapies, curettage, or freezing of warts in the 14 days before screening; in addition, these treatments, or any other over-the-counter wart treatment, should not be implemented during the study. The wash out period for cantharidin, candida antigen, diphencyprone, dinitrochlorobenzene, squaric acid dibutyl ester and any other immunomodulating treatment not otherwise specified is 30 days before the Screening Visit.
 14. Have history of, or current, epidermodysplasia verruciformis
 15. Have an active malignancy or are undergoing treatment for any malignancy
 16. Have a history or presence of hypersensitivity or an idiosyncratic reaction to VP-102 (including cantharidin or related compounds) or study drug product excipients (acetone, ethyl alcohol, nitrocellulose, hydroxypropyl cellulose, castor oil, camphor, gentian violet, and denatonium benzoate)

17. Have a condition or situation that may interfere significantly with the subject's participation in the study (e.g., subjects who required hospitalization within 2 months before screening for an acute or chronic condition including alcohol or drug abuse), at the discretion of the Investigator
18. Are sexually active or may become sexually active and are unwilling to practice responsible birth control methods (e.g., birth control pills, intrauterine device, patch, shot, vaginal ring, and combination of condoms and foam); NOTE that withdrawal and/or sterilization of self or partner are not acceptable methods of birth control. Females that have reached menarche must have a negative urine pregnancy test at each study visit before treatment with study drug
19. Are pregnant or breastfeeding

7.3 Requalification for Entry

Subjects not fulfilling the entry criteria and not randomized may be rescreened for participation if their eligibility characteristics have changed.

7.4 Subject Withdrawal Criteria

Subjects are encouraged to complete the study, but can withdraw consent at any time during the study and for any reason without any penalty or changes to care. The Investigator will provide a written explanation of the reason for discontinuation in a source document and this information will also be recorded on the appropriate electronic case report form (eCRF) page. If a subject withdraws before completion, every effort should be made to complete the EOS (Study Day 147) assessments scheduled during the EOS visit.

A subject may be withdrawn from the study for the reasons described in Section 7.4.1 through Section 7.4.5.

Data collected to the point that the subject withdraws or is withdrawn are still assessable by the Investigator. If subjects do not want their data that has already been submitted, they will need to submit a request in writing to the Investigator for removal of their information.

7.4.1 Adverse Event

If a subject experiences an AE that, in the judgment of the Investigator, the Sponsor, or the Medical Monitor, presents an unacceptable consequence or risk to the subject, the subject may be discontinued from the study.

7.4.2 Intercurrent Illness

A subject may be discontinued from the study if, in the judgment of the Investigator, the subject develops an intercurrent illness or complication that is not consistent with the protocol requirements or that, in any way, justifies withdrawal from the study.

7.4.3 Noncompliance

After the Investigator, the Medical Monitor and/or Study Monitor consult (and the Sponsor if appropriate), a subject may be discontinued from the study for the following administrative reasons:

- Failure to receive study medication or treatment as mandated by the specific instructions provided in [Section 8.0](#).
- Failure to comply with protocol requirements

7.4.4 Refusal of Investigational Product Administration

Any subject refusing clinical trial material for any reason will be discontinued from the study, and the reason(s) for their discontinuation will be documented on the appropriate eCRF page. Reasonable efforts should be made to monitor the subject for AEs and to complete follow-up assessments after treatment discontinuation. These efforts should be documented on the appropriate eCRF page.

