10.8 Risks for Women of Child-bearing Potential or During Pregnancy

The risks of VP-102 application during pregnancy have not been evaluated. Pregnant or lactating females who are nursing are excluded from this study.

Female and male subjects must be instructed to inform the Investigator *immediately* if they become pregnant or genetically contribute to a pregnancy during the study. Should study personnel become aware of a subject's (or subject's partner's) pregnancy, the site personnel must report the pregnancy to the Sponsor's Medical Monitor within 24 hours by using the pregnancy notification form. The female subject will discontinue study drug. The pregnancy will be followed until the outcome is known and will be reported to the Sponsor.

Pregnancy is not an AE, in and of itself. However, any pregnancy complication or elective termination of a pregnancy for medical reasons will be recorded as an AE or SAE. A spontaneous abortion is always considered an SAE and will be reported as described in the AE and SAE sections. Furthermore, any SAE occurring as an adverse pregnancy outcome post-study must be reported to the Medical Monitor.

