7.1. Subject Disposition

The number of subjects randomized and number of subjects in each population will be summarized by treatment group. Also included will be the number of subjects who completed through Day 84, number of subjects assessed for clearance at Day 84 based on analysis windows, number of subjects with major protocol violations, number of subjects who received all planned treatments of study drug by Day 75 or achieved complete clearance prior to Day 75, number of subjects completing and discontinuing the study, along with the primary reason for discontinuation. The completion/discontinuation status refers to the subject's participation in the study; therefore, the data is collected at the last

scheduled visit, Study Day 147 EOS. If a subject discontinues the study prematurely, then the case report form is completed at the time of discontinuation.

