8.4. Handling of Dropouts or Missing Data

All subjects who were randomized will be evaluated in the ITT population. If a subject requests to be removed from the study due to study related adverse events or additional spreading of disease, data will be collected and analyzed as a treatment failure and not replaced. If a subject discontinues use of study drug but remains in the study, the subject will be analyzed as a non-responder as well. Per the study protocol, subjects who achieve complete clearance of all lesions prior to Day 84 are required to attend all Treatment Visits but will not receive treatment at those visits where all lesions are clear. These subjects will not be considered as having prematurely discontinued use of the study drug.

Unless described otherwise in subsequent sections, analyses will be carried out with the data available using no imputation for missing data. A description of how missing data will be handled for select endpoints is included below.

8.4.1. Coronavirus 19

Due to the coronavirus 19 (COVID-19) outbreak during the course of the study, there may be several subjects who will have missing assessments which could affect the primary analysis. Subjects who are unable to attend a study visit due to COVID-19 will be documented in the protocol deviation log. The protocol deviation date will be used as the COVID-19 affected date (or visit). If a subject reports an adverse event of COVID-19, then the event start date will be used as the affected date. In the event that a subject has an affected COVID-19 date from both sources, the earlier of the dates will be used.

Subjects who were affected by COVID-19 will be summarized in a data listing. The listing will contain the following information: subject number, treatment, gender, age, first date affected by COVID-19, duration in study prior to the affected COVID-19 date, total study duration, exposure to study drug, any COVID-19 related adverse events, completion/discontinuation of the study, and reasons for discontinuation. All data listings will include a flag to denote whether the subject and/or visit was affected by COVID-19.

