8.4.3. Handling of Missing Data for Treatable Wart Count Endpoints

Assessment of number of treatable warts is planned for the baseline visit, the EOT visit, follow-up visits (including EOS), and each treatment visit. Endpoints that are based on these assessments include percent reduction from baseline of treatable warts, change from baseline in treatable warts, percent reduction from baseline in total wart area, change from baseline in total wart area, and proportion of subjects exhibiting reduction of at least 1 treatable wart from baseline. No imputation will be done on missing data for these endpoints.

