9.2. Change and Percent Change in Number of Warts

Number of warts present will be recorded at each treatment visit as well as follow-up visits. For each post baseline treatment visit, the change in number of warts from baseline will be calculated. Summary statistics of number of warts will be displayed for each treatment visit. Summary statistics of change in number of warts from baseline will also be displayed. Statistical analyses on each treatment regimen will be performed. A restricted maximum likelihood-based repeated-measures approach, using a Mixed effect Model Repeat Measurement (MMRM) will be used. The MMRM model will include the fixed, categorical effects of treatment, gender, visit, and treatment-by-visit interaction as well as the continuous, fixed covariate of baseline wart count. An unstructured (co)variance structure shared across treatment groups will be used to model the within-subject errors. If convergence is not met, then the Akaike's Information Criteria will be used to select the best covariance structure to model the data. The Kenward-Roger approximation will be used to estimate denominator degrees of freedom and adjust standard errors.

Percent change of warts will be calculated at each post baseline visit. Percent change will be calculated using the following formula (in formula below, warts refers to treatable warts):

$$\text{Percent (\%) Change} = \frac{(\text{Warts}_{\text{Visit}} - \text{Warts}_{\text{Baseline}}) / \text{Warts}_{\text{Baseline}}}{1} * 100$$

Analysis of percent change in number of warts will be carried out in the same manner as change in number of warts.

An additional analysis will be carried out by visit to report the number and percent of subjects who had a reduction of one or more treatable warts from baseline. The proportion of subjects with 90% and 75% clearance of warts will also be analyzed using a CMH test.

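### Protocol 7.4.4 takes a subject who refuses study drug off the study, so wart counts and areas at Day 84, Day 112 and possibly Day 147 may be lost without need (minor)

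*Protocol*

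**What the plan says.** Protocol 7.4.4 sets the rule for refusal: "Any subject refusing clinical trial material for any reason will be discontinued from the study". The section goes on: "Reasonable efforts should be made to monitor the subject for AEs and to complete follow-up assessments after treatment discontinuation". It ends by requiring that these efforts be documented on the eCRF. It names no visit or day.

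The general rule in Protocol 7.4 is: "If a subject withdraws before completion, every effort should be made to complete the EOS (Study Day 147) assessments scheduled during the EOS visit". It does not mention Day 84 or Day 112. Table 1 has no early-termination column. On the status form, SAP 7.1 says: "If a subject discontinues the study prematurely, then the case report form is completed at the time of discontinuation".

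Elsewhere the documents do separate stopping drug from leaving the study. Protocol 10.8, on pregnancy, says: "The female subject will discontinue study drug". SAP 8.4 says: "If a subject discontinues use of study drug but remains in the study, the subject will be analyzed as a non-responder as well".

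For change and percent change in wart count, change and percent change in wart area, and reduction of at least one wart, SAP 8.4.3 says: "No imputation will be done on missing data for these endpoints". For the change in wart count, SAP 9.2 says: "A restricted maximum likelihood-based repeated-measures approach, using a Mixed effect Model Repeat Measurement (MMRM) will be used". Wart area is summarized descriptively (SAP 9.3).

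**The concern.** Declining a further application of a vesicant is a treatment decision. It need not mean that the subject objects to having warts counted. Protocol 7.4.4 nevertheless makes study discontinuation mandatory. The adverse-event, intercurrent-illness and noncompliance rules (7.4.1 to 7.4.3) only permit it, and the one other mandatory rule in the group is withdrawal of consent (7.4.5). A refuser who would gladly attend Day 84 is therefore classed with someone who has withdrawn consent.

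The second sentence of 7.4.4 points the other way, because follow-up assessments after treatment has stopped suit a subject who is off drug but still observed. Which visits take place then depends on how each site reads the paragraph.

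Part B is meant to identify the regimen with the better balance of risk and benefit. What happens to warts in people who will not accept another application bears on that choice. If their later counts and areas are missing and not imputed, the regimen comparison may rest on those who tolerated treatment.

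**Working it through.** There is no planned figure to reproduce: the documents give no power calculation and no refusal or dropout rate. The check counts what is lost per refuser, then scales it under a stated assumption.

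**Inputs.** Post-baseline wart counts are scheduled at Visits 2, 3 and 4 and Days 84, 112 and 147, which makes 6 (SAP 8.1). Post-baseline areas are scheduled at Days 84, 112 and 147, which makes 3 (SAP 9.3). SAP 8 uses a treatment visit in by-visit summaries only if treatment was given. The count at the refusal visit and at later untreated treatment visits is therefore unused whatever 7.4.4 says, and is not charged to it.

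**Usable post-baseline counts out of 6, by visit of refusal:**

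| Refusal at | All three later visits kept | Only Day 147 obtained | Closed out at once |
|---|---|---|---|
| Visit 2 | 0 + 3 = 3 | 0 + 1 = 1 | 0 |
| Visit 3 | 1 + 3 = 4 | 1 + 1 = 2 | 1 |
| Visit 4 | 2 + 3 = 5 | 2 + 1 = 3 | 2 |
| Counts lost | 0 of 6 | 2 of 6 | 3 of 6 |
| Areas lost | 0 of 3 | 2 of 3 | 3 of 3 |

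A Visit 2 refuser who is closed out has no usable post-baseline count and adds nothing to the estimated change from baseline in the repeated-measures model.

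**Arm sizes.** Part B allocates 90 subjects 3:3:2:2, and Part A adds 5 VP-102 and 1 placebo subject to each selected regimen. Pooled VP-102 arm: 90 × 3/10 + 5 = 32. Matching placebo arm: 90 × 2/10 + 1 = 19.

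**Scale (assumption: m = 0 to 5 refusers without a Day 84 visit in one VP-102 arm, none in its placebo arm).** The Day 84 share missing is m/32. For a simple two-group contrast with equal variances, the standard error changes by the factor √[(1/(32 − m) + 1/19) / (1/32 + 1/19)].

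| m | Day 84 missing in arm | SE factor |
|---|---|---|
| 0 | 0% | 1.000 |
| 1 | 3.1% | 1.006 |
| 5 | 15.6% | 1.034 |

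The loss of precision is small. What matters is who is missing.

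**One illustration of selection (assumed figures).** SAP 5 leaves missing values out of percentages unless stated otherwise. Suppose 15 of 32 have at least one wart fewer and 5 others are refusers. If the refusers are retained and SAP 8.4 makes them non-responders on this endpoint, the rate is 15/32 = 47%. If they are closed out and leave the denominator, it is 15/27 = 56%. This needs the SAP 8.4 non-responder rule to reach this endpoint. It also needs the closed-out refusers not to fall under the separate SAP 8.4 rule that counts as failures those who ask to leave because of study-related adverse events or spreading disease.

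**Primary endpoint.** A refuser who stays is a non-responder (SAP 8.4). One who leaves has no Day 84 assessment and counts as not cleared (SAP 8.4.2; Protocol 7.6). The main ITT result is the same either way.

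**The case against.** The strongest reply is that 7.4.4 largely repairs itself. It asks for follow-up assessments and requires the efforts to be documented, so a site that closes a refuser out with no recorded attempt is not following the section. Protocol 7.4 asks for every effort on the Day 147 assessments, so the literal reading costs 2 of 6 counts and 2 of 3 areas, and the full loss is a worst case. This stands, and it lowers the size of the point. It does not remove it: the efforts are only best efforts, no visit is named in 7.4.4, and neither section asks for Day 84 or Day 112.

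The range of 0 to 5 refusers has no source in the documents, and the standard-error factor describes a simple contrast, not the planned model. Both are fair, and the figures serve for scale only.

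A reader might go further in four ways that the documents do not support:

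- That SAP 8.4 contradicts 7.4.4. It does not. Subjects who stop drug for other reasons, such as pregnancy under Protocol 10.8, can fill its off-drug, on-study category.
- That SAP 7.1 orders immediate close-out. It fixes when a status form is completed; it does not end data collection.
- That late local skin reactions would drop out of the safety tables through the end-of-study cut-off in Protocol 12.4. That needs an early end-of-study visit, which neither document describes. Protocol 10.2.1 has adverse events noted to Day 147 and includes periods without drug, 10.7 requires follow-up of reported events, and SAP 10.2 has no such cut-off. The 24-hour, 7-day and 14-day calls also normally precede the next treatment visit, where refusal would usually arise.
- That refusals would concentrate in the VP-102 arms. It is plausible for a blistering agent, but nothing in the documents shows it.

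**Conclusion.** The point holds as a minor one. Protocol 7.4.4 makes leaving the study mandatory on refusal of drug, while its own next sentences and SAP 8.4 assume that people can be off drug and still followed. Per refuser the loss runs from nothing, through 2 of 6 counts and 2 of 3 areas, to 3 of 6 and 3 of 3, depending on how far the requested follow-up succeeds.

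The exposed analyses are the wart-count model, the wart-area summaries and the proportion with at least one wart fewer, none of which has imputation. They are secondary or exploratory, and SAP 8.6 calls every comparison exploratory. The main clearance analysis at Day 84 is essentially unaffected, so a reader should not infer bias there. With up to 5 such refusers in an arm of 32, which is an assumption, precision falls by about 3% at most. The remaining risk is selective missingness in the choice of regimen. Its size and direction cannot be determined from the documents, and it could be zero.

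**What to change.** Reword Protocol 7.4.4 along these lines: *A subject who declines study drug will be recorded as having discontinued study drug. Unless consent is withdrawn, the subject will remain in the study and attend the Day 84, Day 112 and Day 147 visits in Table 1.* Add an eCRF item that separates off drug from off study.

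Nothing else needs to move. The SAP 8.4 non-responder rule already covers these subjects, the SAP 8 rule on untreated visits can stay, and Protocol 12.4 needs no amendment.

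The cost is a short amendment to one section and one eCRF distinction. The three visits are already scheduled. The downside is that sites go on seeing subjects who have declined the drug.
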